4.3.2 Laboratory Variables

Laboratory assessments will be performed by a central laboratory, as identified in the List of Study Personnel. Please see the Laboratory Manual for detailed instructions regarding the collection, processing, and handling of laboratory samples.

The laboratory variables presented in **Table 1** will be assessed in accordance with the Schedule of Assessments (**Table 2**). Routine laboratory tests (serum chemistry [including electrolytes], hematology, and urinalysis) will be performed at each study visit, from Screening to Posttreatment. A 6- to 12-hour fast is advised for Visit 1 and is highly recommended prior to all visits when blood sampling is scheduled. The timing of other safety tests (e.g., pregnancy tests and drug screen) is presented in the Schedule of Assessments (**Table 2**).

Table 1 Laboratory Assessments

Hematology:	Erythrocytes, mean corpuscular volume (MCV), mean corpuscular hemoglobin (MCH), neutrophils, eosinophils, basophils, lymphocytes, monocytes, platelets, leukocytes, hemoglobin, and hematocrit
Urinalysis:	Specific gravity, pH, protein, glucose, ketones, blood, and microscopic examination of sediment
Serum chemistry:	Alanine aminotransferase, aspartate aminotransferase, creatinine, alkaline phosphatase, total bilirubin, direct bilirubin, blood urea nitrogen, total protein, albumin, uric acid, glucose, and cholesterol.
Hormone:	TSH at screening to determine eligibility (T3 and free T4 if TSH is out of range)
Electrolytes:	Sodium, potassium, chloride, magnesium, phosphorus, calcium
Pregnancy test:	Urine pregnancy tests via dip sticks (performed on-site)
Immunogenicity:	Anti-plecanatide antibody serum assessment
PK:	Plecanatide (and SP-338) plasma assessment
Urine screen for select opioids:	Methadone, morphine, and oxycodone.

At Screening, any laboratory abnormality considered clinically significant by the Investigator or the Medical Monitor will render the patient ineligible for study enrollment.

Approximately 2.0 mL of blood will be drawn for each hematology sample and approximately 5.0 mL of blood will be drawn for each serum chemistry sample. The volume of blood that will be required for these laboratory tests during the duration of the study, not including possible repeat tests, will be approximately 28 mL.

4.3.3 Immunogenicity and Pharmacokinetic (PK) Assessments

Approximately 3.5 mL of blood for immunogenicity testing – measurement of serum concentration of anti-plecanatide antibodies, will be collected (and banked) from all patients, as specified in the Schedule of Assessments. The total volume of blood required for immunogenicity testing during the study will be approximately 11 mL.

Blood samples (6 mL each) for measurement of plecanatide and SP-338 concentration will be collected from all patients on Day 1 of the Treatment Period (15 min prior to dosing) and at the Week 4 and Week 8 visits. Intensive sampling for formal PK analysis will be conducted in a subgroup of approximately 40 patients (10 patients per each treatment group) who consent to the additional blood sampling at 30, 60, 90, and 120 minutes following study drug administration on Day 1 of treatment. The actual sampling times will be recorded on the eCRF for each PK sample. The total blood volume collected for PK analysis will be about 18 mL for the majority of patients, and 42 mL for patients participating in the intensive PK analysis. Only samples from patients randomized to active treatment will be analyzed.

Orally delivered plecanatide is not absorbed in the adult population nor is it expected to be absorbed in the 12 to <18-year-old age group. However, should any measurable levels of plecanatide or its primary metabolite (SP-338) be observed, to the extent possible, pharmacokinetic parameter estimates (C_{max} , C_{min} , t_{max}) will be undertaken. Nominal sampling time will be used for all parameter estimation.

In order to maintain the double-blind status of the study, results of the pharmacokinetic assay will be blinded to the investigators, to the sponsor, and monitors during the course of the study.

The procedure for the collection, handling, storage, and shipment of the samples for PK and immunogenicity analysis are specified in the site reference laboratory manual.

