Statistical Methods	
Analysis Populations
 
Analysis populations include the Safety population, the Intent-to-treat (ITT) population, and the Per-Protocol (PP) population. The Safety population will include all patients who were randomly assigned to a treatment group and received at least 1 dose of study drug. The ITT population will include all patients who were randomized to receive study drug. The PP population will be used for sensitivity analyses, and will consist of all patients in the ITT population without any significant protocol violations. The ITT population will be the primary population for efficacy analyses.
 
Patient Characteristics and Disposition
 
Demographic characteristics (including age, gender, race, weight, height, and body mass index) and characteristics of patients' CIC history will be summarized by descriptive statistics for each treatment group.
 
Efficacy Analyses
 
Primary Efficacy Analysis
 
The primary efficacy endpoint is the proportion of responders for the last 2 weeks of the Treatment Period (responder = a child who experiences >3 SBMs per week for each of the last two weeks of the treatment period) compared to placebo and across treatment groups. The change from baseline in mean weekly SBM rate will be analyzed using a linear mixed-effects model with fixed effects for gender (stratification variable), treatment, week, and the corresponding baseline value; a random intercept for patient will also be specified. The least squares (LS) mean change from baseline will be presented, by treatment group, and the difference in LS means for each plecanatide treatment group compared to placebo will be presented, with 95% confidence intervals and corresponding statistical p-values.
 
Secondary Efficacy Analysis
 
The secondary efficacy endpoints are:
 
• Change from baseline in weekly average stool consistency (BSFS) score over the 8-week treatment period, and by study week• Change from baseline in the weekly rate of SBMs, by study week• Change from baseline in the weekly rate of CSBMs over the 8-week treatment period, and by study week 
The mean in each period and the change from baseline will be summarized in each treatment group. Differences between treatment groups will be analyzed with an analysis of covariance, including fixed effects for gender (stratification variable) and treatment and corresponding baseline value as a covariate. A least squares mean with 95% confidence intervals will be presented for the difference between each plecanatide group and placebo.
 
Pharmacokinetic Analyses
 
Plasma plecanatide (and its major metabolite SP-338) concentrations will be assessed for all patients pre-dose on Day 1, and at Week 4 and Week 8 visits.

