2.4.2 Pharmacokinetic Endpoints

Single dose and steady state PK of plecanatide and its major metabolite SP-338 (population modeling):

- Plasma concentration of plecanatide and SP-338 (Note: measurable plecanatide/SP-338 levels have not been observed in the adult population)
- PK parameters, including C_{max} , T_{max} , and C_{min} (only if sufficient number of plecanatide levels can be measured to allow computation of these parameters)

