5 STUDY CONDUCT

5.1 SCHEDULE OF ASSESSMENTS

Patients will provide written informed consent before any study-related procedures are initiated, including the cessation of prohibited concomitant therapy.

For the timing of assessments and procedures throughout the study, refer to the Schedule of Assessments **Table 2**. Throughout the study, every reasonable effort should be made by study personnel to follow the timing of assessments and procedures in the Schedule of Assessments for each patient. If a patient misses a study visit for any reason, the visit should be rescheduled as soon as possible.

Table 2 Schedule of Assessments

Study Period Visit Study Week	Screening/ Baseline	Treatment			Post-treatment Follow-up Visit 5 Week 10(EOS)
		Visit 1 Week -4	Visit 2 Week 1	Visit 3 Week 4	
		Day -28	Day 1	Day 28±3	
Informed Consent/Accent	X				
Inclusion/Exclusion Criteria	X	X			
Demography	X				
Medical History (including GI and bowel habits)	X	X			
Prior and Concomitant Medications/Diet	X	X	X	X	X
Physical Examination ^a	X	X	X	X	X
Vital Signs ^b	X	X	X	X	X
Pregnancy Test (urine) ^c	X	X	X	X	X
Urine Drug Screen for Opioids ^d	X	X			
Serum Chemistry, Hematology, Urinalysis	X	X	X	X	
TSH (include T3 and T4 only if TSH is abnormal)		X			
Immunogenicity Test (serum collection)		X	X	X	
Plecanatide/SP-338 Concentration ^e (plasma collection)		X ^e	X	X	
PK Sampling (30, 60, 90 and 120 mins post-dose in a subset of patients)		X			
12-lead Electrocardiogram ^f	X	X*		X	
Electronic Diary Training and Activation ^g	X				
Diary Eligibility ^h / Compliance Check		X ^h	X	X	
Randomization		X			
Study Drug Dispensation and Administration ⁱ		X	X		

Study Period Visit Study Week Visit Day (Window)	Screening/ Baseline	Treatment			Post-treatment Follow-up
	Visit 1 Week -4	Visit 2 Week 1	Visit 3 Week 4	Visit 4 Week 8(EOT) or EW	Visit 5 Week 10(EOS)
	Day -28	Day 1	Day 28±3	Day 56 +3	Day 70 +3
At Visit PRO Assessments ^j	X	X	X	X	X
Study Drug Collection and Accountability			X	X	X
Rescue Medication Dispensation	X	X	X	X	
Adverse Events ^k	X	X	X	X	X

EOT = end of treatment; EW = early withdrawal; EOS = end of study; GI = gastrointestinal; PK = pharmacokinetic; TSH = thyroid-stimulating hormone.

- a. Physical examination, including body weight measurement, will be performed at Visits 1 to 4 and EW; height is measured (and body mass index calculated) at the Screening Visit only.

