- b. Seated blood pressure (after patient has been seated for at least 5 minutes), heart rate, respiration, temperature.
- c. Urine pregnancy test will be performed on-site for female patients; negative result must be confirmed at Screening and Day 1 prior to randomization.
- d. Urine drug screen for selected opioids (screen includes methadone, morphine and oxycodone) will be performed on-site; a negative result must be confirmed prior to dispensing the study medication.
- e. 15 mins before study drug dosing.
- f. The standard 12-lead ECG will be performed in the semi-recumbent or supine position. (*) At Visit 2 (Week 1/Day 1), ECG will be performed prior to study drug dosing and again one hour after the study drug administration.
- g. Clinical site personnel will train patients on the use of electronic diaries at the Screening visit and remind them to make daily entries throughout the study, with retraining as needed. The interactive voice or web response system will provide daily reminders to improve compliance.
- h. Baseline diary results will be reviewed programmatically and a “Diary Eligible” or “Not Diary Eligible” report will be provided to the site immediately prior to randomization.
- i. Patients will take their first dose of study drug at the site on Day 1; it is recommended that for dosing at home, patients take it once daily at approximately the same time in the morning.
- j. Details on timing of each PRO Assessments will be included in the Study Procedure Manual.
- k. Adverse Event collection begins immediately after informed consent is signed. A symptom-directed physical examination should be performed as appropriate at discretion of the investigator.

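### PK parameters are tied to nominal sampling times although actual times are recorded, and the timing of the Week 4, Week 8 and Early Withdrawal samples relative to dose cannot be established

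*Combined protocol and SAP*

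**What the plan says.** Protocol Section 4.3.3 collects one time variable and analyses another. It first says "The actual sampling times will be recorded on the eCRF for each PK sample", and later, of the Cmax, Cmin and Tmax estimates, "Nominal sampling time will be used for all parameter estimation".

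Section 2.4.2 makes single-dose and steady-state pharmacokinetics of plecanatide and SP-338 an endpoint, to be obtained by population modelling. Parameters are computed only if enough levels can be measured. Section 8.9 mentions only a listing by patient and a summary by treatment group.

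On sampling times:

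- **All patients:** Section 4.3.3 places samples "on Day 1 of the Treatment Period (15 min prior to dosing) and at the Week 4 and Week 8 visits". The synopsis likewise says that "concentrations will be assessed for all patients pre-dose on Day 1, and at Week 4 and Week 8 visits".
- **Intensive subset (about 40 patients, 10 per group):** "additional blood sampling at 30, 60, 90, and 120 minutes following study drug administration on Day 1 of treatment".
- **Table 2:** a footnote putting the sample 15 minutes ahead of the dose (footnote e) is attached both to the row label "Plecanatide/SP-338 Concentration" and to the Day 1 cell. The Week 4 and Week 8 cells carry a plain mark.
- **Early Withdrawal:** Section 5.2.6 lists a PK sample at a visit that may fall up to 5 days after the patient stops study drug. Table 2 gives this visit the same column as Week 8.

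On dose times, Section 5.2.2 has the first dose supervised at the site and its time recorded. For later doses, Table 2 footnote i says only that "it is recommended that for dosing at home, patients take it once daily at approximately the same time in the morning".

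**The concern.** Two separate weaknesses bear on the same endpoint.

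First, Tmax is itself a time, and a population model is fitted to concentrations against elapsed time. Setting aside a recorded time in favour of a scheduled one adds avoidable error to both.

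Second, Weeks 4 and 8 supply the only scheduled on-treatment samples after Day 1, so anything said about steady state, including a steady-state Cmin, rests on them. If time since dose is unknown, a measurable level cannot be called a trough. A level below the assay limit is also weaker evidence of no absorption, because the reader cannot tell whether it was drawn soon after a dose or about a day later. The blood is drawn to test in adolescents an expectation carried over from adults, so the negative results matter too.

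**Working it through.** **1. Confirm the sampling scheme from the stated blood volumes.** Section 4.3.3 gives 6 mL per PK sample and totals of 18 mL (most patients) and 42 mL (intensive subset).

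- Routine: 3 samples × 6 mL = 18 mL.
- Intensive: (3 + 4) × 6 mL = 42 mL.
- With 28 mL for safety tests and 11 mL for immunogenicity: 28 + 11 + 18 = 57 mL and 28 + 11 + 42 = 81 mL, the totals in Section 2.3.

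The figures reproduce, so one PK sample each on Day 1, Week 4 and Week 8 is intended. The Visit 3 (Week 4) list in Section 5.2.3 names blood for immunogenicity only and therefore conflicts with Section 4.3.3 and Table 2. The Visit 4 list does include the PK sample.

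**2. Set scheduled times beside recorded dose times.**

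| Sample | Time relative to dose in the protocol | Dose time stated to be recorded? |
|---|---|---|
| Day 1, all patients | 15 min before | Yes |
| Day 1, intensive subset | 30, 60, 90, 120 min after | Yes |
| Week 4 and Week 8 | Visit only; pre-dose if footnote e governs the whole row | No |
| Early Withdrawal | None; up to 5 days (5 × 24 = 120 h) after stopping | No |

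Nothing else settles the Week 4 and Week 8 rows. The visit lists (Sections 5.2.3 and 5.2.4) contain no last-dose time. Fasting is recommended before blood draws (Section 4.3.2), but the tablet may be taken with or without food (Section 6.2). The diary outline in Appendix D asks for the clock time of rescue laxative but has no item for study drug. Without footnote e, time since dose could run from shortly after the morning tablet to about 24 h.

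**3. What the nominal-time rule changes.**

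- Observed Cmax and Cmin are concentrations. Relabelling the time of a sample leaves them as they are.
- Tmax is off by exactly the deviation of the peak sample from schedule, and by zero if that sample was on time.
- A population model takes in the deviation of every sample it uses.

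**4. Illustrative size for Tmax.** The protocol states no sampling window, so deviations of 5, 10 and 15 minutes are assumed. Error = deviation ÷ nominal time.

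| Nominal time | 5 min | 10 min | 15 min |
|---|---|---|---|
| 30 min | 16.7% | 33.3% | 50.0% |
| 60 min | 8.3% | 16.7% | 25.0% |
| 90 min | 5.6% | 11.1% | 16.7% |
| 120 min | 4.2% | 8.3% | 12.5% |

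**5. How many samples fall on each side.** Only active-arm samples are analysed.

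- Timed post-dose samples on Day 1: 3 active groups × 10 patients × 4 = 120.
- Week 4 and Week 8 samples with unestablished time since dose: 3 × 30 patients × 2 = 180 at most, if nobody withdraws.

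**The case against.** The strongest case against is that very little depends on this. Parameters are conditional on measurable levels, none are expected, Section 8.9 promises only listings and summaries, and no efficacy conclusion uses PK. That stands, and it makes the point minor. It does not remove the point: Section 4.3.3 states a rule rather than leaving a gap, and below-limit results also need a time since dose to be interpreted.

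It can also be said that the formal SAP foreseen in Section 8 may replace the nominal-time rule. It may, but it cannot recover home-dose times that were never collected. The laboratory manual cited in Section 4.3.3 was not available and may define the visit samples more closely; the protocol itself does not.

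Three stronger readings are tempting, and the documents do not support them.

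- A reader might infer that every measured level would be placed at the wrong time. Day 1 samples have set times around a supervised, timed dose, so their error is only the deviation from schedule. A 10-minute shift is also smaller than the 30-minute grid that already limits Tmax.
- A reader might infer that nominal timing makes Cmin wrong. It does not alter the observed value. The difficulty is calling a sample a trough when its timing is unconfirmed.
- A reader might infer that Weeks 4 and 8 plainly have no nominal time. Footnote e on the row label allows a pre-dose reading, which would suit a Cmin endpoint. The second marker on the Day 1 cell makes that uncertain, so the timing is ambiguous rather than absent.

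**Conclusion.** The point holds in two parts, both minor.

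1. Parameter estimation is tied to nominal time for no stated reason when actual time is on the eCRF. Only Tmax and model-based estimates are affected, by the deviation from schedule, and only if levels are measurable. The percentages above rest on assumed deviations and are illustrations.
2. The timing of the Week 4 and Week 8 samples relative to dose is ambiguous, and the preceding home dose is not stated to be timed. Up to 180 active-arm samples cannot be confirmed as troughs or placed in time since dose. The Early Withdrawal sample shares the gap and can sit under the same visit label as Week 8. The 120 timed post-dose samples on Day 1 are not touched by this second part, and they remain the main evidence on absorption.

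No figure can be put on how far a mistimed Week 4 or Week 8 sample would stand above a true trough, because the documents give neither a half-life nor a peak time. Assuming a half-life of 0.5 to 2 h, a sample 2 h after dose would hold 2^(−2/0.5) = 6% to 2^(−2/2) = 50% of peak if the peak came at time zero. It would hold 2^(−1/0.5) = 25% to 2^(−1/2) = 71% if the peak came at 1 h, and 100% if it came at 2 h. That span shows only that the size is unknown.

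**What to change.** - In Section 4.3.3, use actual elapsed time since the last dose for all parameter estimation, and keep nominal time for summaries by time point.
- Add an eCRF field for the date and clock time of the last dose before each Week 4, Week 8 and Early Withdrawal PK sample. List concentrations against elapsed time, with Early Withdrawal samples identifiable apart from Week 8.
- Label a sample Cmin only when it is confirmed as pre-dose.
- State the intended timing of the Week 4 and Week 8 samples relative to dose, and reconcile Table 2 footnote e and the Visit 3 list in Section 5.2.3 with Section 4.3.3.

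The cost is a few sentences, one eCRF field and minor listing work. No additional blood is needed. The field has to be in place before the first Week 4 visit (or any Early Withdrawal visit before it), since the dose times cannot be reconstructed at analysis.

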4.3.4 Vital Signs

The following vital signs will be assessed in accordance with the Schedule of Assessments (**Table 2**). Measurements should be performed after the patient has been seated for at least 5 minutes. A clinically significant abnormality at screening may result in the patient being excluded from the study.

- Blood pressure (systolic and diastolic; mmHg)
- Heart rate (beats per minute)
- Oral body temperature (°C)
- Respiration rate (breaths per minute)

4.3.5 Electrocardiograms

Standard 12-lead ECGs will be performed in accordance with the Schedule of Assessments (**Table 2**). A clinically significant abnormality at Screening, as determined by the PI, will result in the patient being excluded from the study.

4.3.6 Physical Examinations

Physical examinations (PEs) will be performed in accordance with the Schedule of Assessments (**Table 2**). A clinically significant abnormality at Screening may result in the patient being excluded from the study.

The PE will be based on the following body systems: general appearance, head (ear, eyes, nose, and throat), cardiovascular, respiratory system, abdomen, musculoskeletal, neurological, lymph nodes, and skin.

Neither a urogenital exam nor a digital rectal examination is required for the study but should take place at Screening if the Investigator feels that there may be a confounding factor for constipation symptoms e.g., anal pathology, or a rectocele in a female patient.

NOTE: The presence of other alarm symptoms (lower GI bleeding, iron-deficiency anemia, unexplained clinically-significant weight loss and systemic signs of infection or colitis) preclude patient eligibility for this trial, unless the PI has adequately assessed each alarm symptom and has discussed their medical relevance with the Medical Monitor, including the potential need for colonoscopic evaluation of the symptoms.

Height will be measured at the Screening Visit only. Weight will be measured as part of all physical examinations; the same calibrated scale should be used for each measurement. BMI calculation will use the height and weight recorded at Visit 1 (Screening Visit).

4.3.7 Concomitant Medications and Diet

Concomitant medications or supplements will be reviewed and documented at each study visit to ensure prohibited/restricted substances are not being taken. Concomitant medication will be documented as described in **Section 3.3**.

Drugs required to be at a stable dose prior to screening including thyroid hormone replacement (30-day stabilization) should not be initiated or dose adjusted during the study.

Diet will be reviewed at each study visit to ensure that each patient is maintaining an acceptable and stable diet throughout the study. Any change in diet considered clinically significant by the Investigator will be documented in the eCRF.

4.3.8 Rescue Medication

Use of rescue medication will be reported in the electronic diary. Patients will be instructed to take rescue medication only if 72 hours have elapsed since their last BM and reminded of this instruction at each visit.

5 STUDY CONDUCT

5.1 SCHEDULE OF ASSESSMENTS

Patients will provide written informed consent before any study-related procedures are initiated, including the cessation of prohibited concomitant therapy.

For the timing of assessments and procedures throughout the study, refer to the Schedule of Assessments **Table 2**. Throughout the study, every reasonable effort should be made by study personnel to follow the timing of assessments and procedures in the Schedule of Assessments for each patient. If a patient misses a study visit for any reason, the visit should be rescheduled as soon as possible.

Table 2 Schedule of Assessments

Study Period Visit Study Week	Screening/ Baseline	Treatment			Post-treatment Follow-up Visit 5 Week 10(EOS)
		Visit 1 Week -4	Visit 2 Week 1	Visit 3 Week 4	
		Day -28	Day 1	Day 28±3	
Informed Consent/Accent	X				
Inclusion/Exclusion Criteria	X	X			
Demography	X				
Medical History (including GI and bowel habits)	X	X			
Prior and Concomitant Medications/Diet	X	X	X	X	X
Physical Examination ^a	X	X	X	X	X
Vital Signs ^b	X	X	X	X	X
Pregnancy Test (urine) ^c	X	X	X	X	X
Urine Drug Screen for Opioids ^d	X	X			
Serum Chemistry, Hematology, Urinalysis	X	X	X	X	
TSH (include T3 and T4 only if TSH is abnormal)		X			
Immunogenicity Test (serum collection)		X	X	X	
Plecanatide/SP-338 Concentration ^e (plasma collection)		X ^e	X	X	
PK Sampling (30, 60, 90 and 120 mins post-dose in a subset of patients)		X			
12-lead Electrocardiogram ^f	X	X*		X	
Electronic Diary Training and Activation ^g	X				
Diary Eligibility ^h / Compliance Check		X ^h	X	X	
Randomization		X			
Study Drug Dispensation and Administration ⁱ		X	X		

Study Period Visit Study Week Visit Day (Window)	Screening/ Baseline	Treatment			Post-treatment Follow-up
	Visit 1 Week -4	Visit 2 Week 1	Visit 3 Week 4	Visit 4 Week 8(EOT) or EW	Visit 5 Week 10(EOS)
	Day -28	Day 1	Day 28±3	Day 56 +3	Day 70 +3
At Visit PRO Assessments ^j	X	X	X	X	X
Study Drug Collection and Accountability			X	X	X
Rescue Medication Dispensation	X	X	X	X	
Adverse Events ^k	X	X	X	X	X

EOT = end of treatment; EW = early withdrawal; EOS = end of study; GI = gastrointestinal; PK = pharmacokinetic; TSH = thyroid-stimulating hormone.

- a. Physical examination, including body weight measurement, will be performed at Visits 1 to 4 and EW; height is measured (and body mass index calculated) at the Screening Visit only.
- b. Seated blood pressure (after patient has been seated for at least 5 minutes), heart rate, respiration, temperature.
- c. Urine pregnancy test will be performed on-site for female patients; negative result must be confirmed at Screening and Day 1 prior to randomization.
- d. Urine drug screen for selected opioids (screen includes methadone, morphine and oxycodone) will be performed on-site; a negative result must be confirmed prior to dispensing the study medication.
- e. 15 mins before study drug dosing.
- f. The standard 12-lead ECG will be performed in the semi-recumbent or supine position. (*) At Visit 2 (Week 1/Day 1), ECG will be performed prior to study drug dosing and again one hour after the study drug administration.
- g. Clinical site personnel will train patients on the use of electronic diaries at the Screening visit and remind them to make daily entries throughout the study, with retraining as needed. The interactive voice or web response system will provide daily reminders to improve compliance.
- h. Baseline diary results will be reviewed programmatically and a “Diary Eligible” or “Not Diary Eligible” report will be provided to the site immediately prior to randomization.
- i. Patients will take their first dose of study drug at the site on Day 1; it is recommended that for dosing at home, patients take it once daily at approximately the same time in the morning.
- j. Details on timing of each PRO Assessments will be included in the Study Procedure Manual.
- k. Adverse Event collection begins immediately after informed consent is signed. A symptom-directed physical examination should be performed as appropriate at discretion of the investigator.

